2.5.2 Data handling conventions for secondary efficacy variables

Fasting condition

FPG measurement not collecting in fasting condition will not be used in the analyses.

Invalid laboratory data

HbA1c or FPG measurements flagged as invalid by the laboratory will not be used in the analyses.

Handling of missing data in the calculation of SMPG variables

At least 4 measurements from the 7 points profile are required for analyzing the profile by timepoint, the 24-hour mean SMPG and the corresponding variability.

At least 3 measurements from the 5 points profile are required for analyzing the profile by timepoint.

At least 3 fasting (prebreakfast) SMPG values in the last 7 days are required for calculating the mean of the fasting SMPG.

Patient Reported Outcomes and Clinician Reported Outcomes

Was It Worth It (WIWI)

No total score is calculated. Each item will be analysed separately with all available data ie. with no imputation

Work Productivity and Impairment (WPAI) Questionnaire

See [Appendix D](#)

Overall Study Experience-Participation (OSEP) Questionnaire

For OSEP (Part 1), no total score is calculated. Each item will be analysed separately with all available data ie. with no imputation. For participants with data at one timepoint only – for example, Visit 2-Step 2 but not Visit 12 - they will be excluded from the analysis.

For OSEP (Part 2), no total score is calculated. Each item will be analysed separately with all available data ie. with no imputation.

Resource Use Questionnaire (RUQ)

No total score is calculated. For analysis of average on-treatment RUQ score, all available data will be used and no imputation will be completed. For a participant with only 3 post-baseline RUQ completions, the average for each item will be taken of these 3 scores. For a participant with 10 post-baseline RUQ completions, the average for each item will be taken of these 10 scores.

Overall Study Experience-sites (OSES) Questionnaire

For OSES (Part 1), no total score is calculated. For analysis of average on-treatment OSES (Part 1) time score, all available data will be used and no imputation will be completed. For a participant with only 3 post-baseline OSES-Part 1 completions, the average will be taken of these 3 scores. For a participant with 10 post-baseline OSES-Part 1 completions, the average will be taken of these 10 scores.

For OSES (Part 2), no total score is calculated. Each item will be analysed separately with all available data ie. with no imputation.

Diabetes Treatment Satisfaction Questionnaire DTSQs and DTSQc)

The total treatment satisfaction score is the sum of items 1, 4, 5, 6, 7 and 8.

If no more than 2 out of the 6 questions comprising the total treatment satisfaction score are missing, the total treatment satisfaction score is imputed by calculating the average of the scores from the answered questions, dividing this sum by the number of answered questions and multiplying the average by six.

If items 2 or 3 are not answered, frequency of hypoglycemia or hyperglycemia scores is considered as missing.

Hypoglycemia Fear Survey (HFS-II)

Using an item mean score also makes handling missing data more sensible. Instead of dividing by the entire scale or subscale to compute the item mean, only divide by the number of questions answered. This allows a more reasonable comparison between respondents. However, it is recommended that this technique be used only if more than 75% of the items have responses. This equates to having responses for 25 items if scoring the whole HFS-II, for 12 items if scoring the HFS-B, and for 14 items if scoring the HFS-W. If less than 75% of the data is available, the score for that scale or subscale should be counted as missing as it may not be a true reflection of the participants' behaviors and/or worries.

The Diabetes Distress Scale (DDS)

Minimum number of items required for score calculation (at least 2/3).

Table 1 - PROs: Diabetes related - Missing Data Handling

PRO scales	Score	Number of items included in score derivation	Minimum number of items required for score calculation
DTSQs	Total treatment satisfaction score	6	4
	Perceived frequency of hyperglycemia score	1	1
	Perceived frequency of hypoglycemia score	1	1
DTSQc	Total treatment satisfaction score	6	4
	Perceived frequency of hyperglycemia score	1	1
	Perceived frequency of hypoglycemia score	1	1
HFS-II	total score	33	25
	HFS-B score	15	12
	HFS-W score	18	14
DDS	Emotional Burden score	5	4
	Physician distress score	4	3
	Regimen distress score	5	4
	Interpersonal distress score	3	2
	Total DDS score	17	12

Effect Size

The effect size is defined as: $ES = \text{difference} / SD$ where SD is the standard deviation. Note that there are two main types of effect size:

- Within ES: Calculated at the group level, when focusing on change from baseline.
- Between ES: Calculated when comparing treatments groups.

The within-group ES (WES) indicates if the changes from baseline to the end of treatment are clinically meaningful for each group.

$$WES = \frac{LS \text{ mean change from baseline at timepoint } t}{\text{pooled baseline standard deviation}}$$

The between-group ES (BES) indicates if the mean changes from baseline to the end of treatment are clinically meaningful between groups.

$$BES = \frac{\text{difference in LS means between groups at timepoint } t}{\text{pooled baseline standard deviation}}$$

Cohen's rules for Effect Size (ES) and interpretation

ES < 0.2 : Negligible

0.2 ≤ ES < 0.5 : Small

0.5 ≤ ES < 0.8 : Moderate

ES ≥ 0.8 : Important

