Higher total score reflects greater fear of hypoglycemia. A higher Behavior score reflects greater tendency to avoid hypoglycemia and/or its negative consequences. A higher Worry score reflects higher worry concerning episodes of hypoglycemia and its consequences.

See questionnaire in [Appendix I](#).

Diabetes Distress Scale (DDS)

Diabetes-related distress will be measured using the Diabetes Distress Scale (DDS) at baseline and Week 24 (Visit 12).

The DDS contains 17 items related to potential problem areas that people with diabetes may experience. Patients are asked to consider the degree to which each of the items may have distressed or bothered them during the past month, and respond between 1 (not a problem) and 6 (a very serious problem).

The DDS yields a total diabetes distress score and 4 subscale scores, each addressing a different kind of distress (emotional burden, physician distress, regimen distress, interpersonal distress).

Each score (total and subscales) are presented as an average, by summing the patient's responses to the appropriate items and divide by the number of items in that scale.

In addition, total and subscale scores will be categorized: a mean score 2.0 – 2.9 should be considered 'moderate distress' and a mean score >3.0 should be considered 'high distress'.

See questionnaire in [Appendix J](#).

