2.4.7 Analyses of PRO and ClinRO variables

The analysis of the following endpoints will be conducted on the ITT population, on the 24-week randomized period, ie, using all available post-baseline data, regardless of IMP discontinuation.

No p-value will be provided.

For interpretation of results, Effect Sizes (ES) using Cohen's definition will be calculated in order to interpret changes from baseline to Week 24 in PRO scores.

- Within ES: calculated at the study conduct approach group level, when focusing on changes from baseline
- Between ES: Calculated when comparing study conduct approach groups

The calculation and interpretation of ES is described on [Section 2.5.1](#).

To help the interpretation of PROs and ClinRO, plots will be provided if relevant.

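### The effect-size bands in SAP 2.5.2 are applied to signed values, so as printed every negative effect of 0.2 or more is labelled Negligible, and no interval accompanies the label

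*SAP*

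**What the plan says.** SAP 2.4.7 states that effect sizes "will be calculated in order to interpret changes from baseline to Week 24 in PRO scores" and that no p-value will be given. It refers to 2.5.1 for the calculation, which is in fact in 2.5.2 under Effect Size.

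There, ES is a difference divided by SD, "where SD is the standard deviation". WES is the LS mean change from baseline over the pooled baseline SD. BES is the difference in LS means between groups over the same SD. The SAP says that BES "indicates if the mean changes from baseline to the end of treatment are clinically meaningful between groups", and gives WES the same role within each group.

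The bands are "ES < 0.2 : Negligible", "0.2 ≤ ES < 0.5 : Small", "0.5 ≤ ES < 0.8 : Moderate" and "ES ≥ 0.8 : Important". Neither the formulas nor the bands carry an absolute value, a lower limit, an order of subtraction or a rule on the direction of benefit. Neither 2.4.7 nor 2.5.2 asks for a confidence interval on an effect size.

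The scales run in different directions:
- HFS-II (SAP 2.1.7.5): "Higher total score reflects greater fear of hypoglycemia". A higher worry score likewise means more worry.
- DDS (SAP 2.1.7.5): items run from 1, not a problem, to 6, a very serious problem.
- WPAI-SP (SAP 2.1.7.2): higher percentages are worse.
- DTSQs (SAP 2.4.7.5): total satisfaction runs from 0 to 36, with higher better. The hyper- and hypoglycemia items run from 0, none of the time, to 6, most of the time.

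The opening of SAP section 2 says that the study stopped early with 15 of 150 patients randomized, and that only basic descriptive statistics will be provided.

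**The concern.** A rule that grades a signed ratio but has no lower limit on its bottom band puts all negative values in that band. On scales where a lower score is better, improvement is negative, so no improvement can ever be graded above Negligible. On DTSQs total satisfaction the reverse holds: no deterioration can be. A programmer who codes the bands as written would produce these labels without breaking any instruction.

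BES has a second problem. Because the order of subtraction is not given, the same data can yield +0.9 (Important) or -0.9 (Negligible), depending on which group is subtracted from which.

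The label also stands without any measure of uncertainty. The bands below Important are 0.2 or 0.3 wide in magnitude, so sampling error alone can move an estimate from one band to another. The SAP asks the reader to take the effect size as a sign of clinical meaning.

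**Working it through.** **Design figure.** The plan gives no figure for effect-size precision. Its only design figure is a precision of about 0.37% for HbA1c (SAP 1.3), from SD 1.1 and up to 10% non-evaluable. With 75 x 0.9 = 67.5, so 67 to 68 per arm, the between-group half-width is 1.96 x 1.1 x sqrt(2/n) = 0.370 to 0.372, which matches. The point does not rest on this figure. It supplies the 67 per arm used below, borrowing a non-evaluable rate that is stated for HbA1c only.

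**Step 1: apply the printed bands.**

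| ES | Label as printed | Label by magnitude |
|---|---|---|
| -1.2 | Negligible | Important |
| -0.8 | Negligible | Important |
| -0.5 | Negligible | Moderate |
| -0.2 | Negligible | Small |
| -0.1 | Negligible | Negligible |
| 0.2 | Small | Small |
| 0.8 | Important | Important |

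Positive values and values of magnitude below 0.2 are unaffected. As an illustration with assumed figures, a mean DDS change of -0.6 with a baseline SD of 0.6 to 1.2 gives ES = -0.6/0.6 = -1.0 to -0.6/1.2 = -0.5. By magnitude that is Important to Moderate; as printed it is Negligible.

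**Step 2: sampling error of BES.** Let k be the residual SD divided by the baseline SD. The documents do not give k, so a range of 0.6 to 1.0 is assumed. With the baseline SD treated as fixed:

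SE(BES) = k x sqrt(1/n1 + 1/n2)

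- 67 and 67: sqrt(2/67) = 0.173, so the SE is 0.104 to 0.173.
- 8 and 7 (assumed split of the 15 patients): sqrt(1/8 + 1/7) = 0.518, so the SE is 0.311 to 0.518.

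The chance that the magnitude of BES reaches a cut-off c when the true difference is zero is 2 x (1 - Phi(c/SE)):

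| Cut-off | 67/67, k 0.6 to 1.0 | 8/7, k 0.6 to 1.0 |
|---|---|---|
| 0.2 | 5% to 25% | 52% to 70% |
| 0.5 | under 0.5% | 11% to 33% |
| 0.8 | about 0% | 1% to 12% |

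For example, at 8/7 with k = 1.0, 0.5/0.518 = 0.97, which gives 33%.

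**Step 3: interval width.** The 95% half-width of BES is t(0.975, n1+n2-2) x SE. At 67/67, t = 1.978 gives 0.21 to 0.34. At 8/7, t = 2.160 gives 0.67 to 1.12. For WES, t x k/sqrt(n) gives 0.14 to 0.24 with 67 patients and 0.46 to 0.76 with 8. With 15 patients, the full BES interval is at least 1.34 wide (2 x 0.67) and so spans several bands.

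**The case against.** The strongest objection is that the effect sizes may never be produced. They need LS means from the planned ANCOVA models, and the opening of SAP section 2 restricts reporting to basic descriptive statistics. This stands as a limit on practical impact. That opening does not name the effect sizes, however, and 2.4.7 and 2.5.2 still prescribe them.

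Second, the SAP invokes Cohen's definition and rules, and the labels are words of size, so magnitude was probably meant. That is likely right and makes this an omission rather than a misconceived analysis. Nothing in the SAP states it, and protocol 11.4.3.1.1 and 11.4.3.2.1 do not mention effect sizes, so they cannot repair the rule.

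Third, the direction of most scales is documented elsewhere in the SAP, so a careful reader could recover the meaning of a sign. That helps the reader but does not change the label the rule assigns.

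Some stronger readings are tempting, and the documents do not support them:
- A reader might infer that, with no p-values, the labels are the only means of interpreting the PROs. They are not. SAP 2.4.7 and 2.4.7.5 also plan plots, cumulative distribution functions, and the incidence of DDS scores of 3 or more and of DDS responders. Protocol 11.4 and SAP 2.4.4.3 mention descriptive 95% CIs for endpoints, though these are not carried to the effect size.
- A reader might infer that half of all effects are lost by sign. No source gives the share of effects that will be negative.
- A reader might treat a lower HFS-B score as better. SAP 2.1.7.5 says only that a higher score means a greater tendency to avoid hypoglycemia.
- A reader might take a negative BES on DTSQs to mean that the virtual group did worse. The SAP does not fix the order of subtraction.

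**Conclusion.** The point holds as a defect in a stated rule. Read literally, SAP 2.5.2 labels every negative effect size of magnitude 0.2 or more as Negligible, including improvement on HFS-II total and worry, DDS, WPAI-SP and the DTSQs hyper- and hypoglycemia items, and deterioration on DTSQs total satisfaction. This follows from the printed text and needs no assumption.

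The missing interval is a second, smaller part, and its size does depend on assumptions: k of 0.6 to 1.0, a fixed baseline SD, 67 per arm borrowed from the HbA1c calculation, and an 8/7 split that neither document gives. The upper ends (25% at the planned size; 70%, 33% and 12% at 15 patients) hold only at k = 1.0, so they should not be quoted without the range. At the planned size a chance result of Moderate magnitude is rare. With 15 patients it is not.

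The primary endpoint is untouched. Whether the SAP should describe a ratio to baseline SD as showing clinical meaning is debatable, and the point does not rest on it.

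**What to change.** In SAP 2.5.2:
- Apply the four bands to |ES|.
- Define BES as virtual minus traditional.
- State better or worse separately for each scale. For HFS-B, report only more or less avoidance.
- Report WES and BES with 95% CIs.
- If the opening of section 2 means that no LS-mean models will be run for the 15 patients, mark the effect-size text in 2.4.7 and 2.5.2 as not applicable.

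Withholding a label whenever its interval spans more than one band is not recommended. At 67 per arm the full BES interval is 0.41 to 0.68 wide, against 0.3 for the Small and Moderate bands, so neither label could ever be given. Showing the interval beside the label is enough.

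The cost is a few lines of SAP wording and small additions to the PRO tables. No new data are needed.

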2.5.3 Missing data

For categorical variables, patients with missing data are not included in calculations of percentages unless otherwise specified. When relevant, the number of patients with missing data is presented.

For example, if either a baseline assessment or an endpoint assessment is missing for a particular patient, then the change from baseline at endpoint is missing. Depending upon the assessment, analyses may not include all patients in the analysis population, because certain patients in the intended population may have missing data.

Handling of computation of treatment duration if investigational medicinal product end of treatment date is missing

For the calculation of the treatment duration, the date of the last dose of IMP is equal to the date of last administration reported on the end-of-treatment e-case report form page. If this date is missing, the exposure duration should be left as missing.

The last dose intake should be clearly identified in the e-case report form and should not be approximated by the last returned package date.

Handling of medication missing/partial dates

No imputation of medication start/end dates or times will be performed. If a medication date or time is missing or partially missing and it cannot be determined whether it was taken prior or concomitantly, it will be considered a prior, concomitant, and post-treatment medication.

Handling of adverse events/hypoglycemia with missing or partial date/time of onset

No imputation of adverse event/hypoglycemia dates/times will be performed.

By default all adverse events/hypoglycemia are emergent except if additional information allows to classify otherwise.

Handling of adverse events/hypoglycemia, laboratory data, vital signs when date and time of first investigational medicinal product administration is missing

When the date and time of the first IMP administration is missing, all adverse events/hypoglycemia that occurred on or after the day of randomization should be considered as treatment-emergent adverse events/hypoglycemia. The exposure duration should be kept as missing.

Handling of missing assessment of relationship of adverse events to investigational medicinal product

If the assessment of the relationship to IMP is missing, then the relationship to IMP has to be assumed and the adverse event considered as such in the frequency tables of possibly related adverse events, but no imputation should be done at the data level.

Handling of potentially clinically significant abnormalities

If a patient has a missing baseline he will be grouped in the category “normal/missing at baseline.”

For PCSAs with 2 conditions, one based on a change from baseline value or a normal range and the other on a threshold value, with the first condition being missing, the PCSA will be based only on the second condition.

For a PCSA defined on a threshold and/or a normal range, this PCSA will be derived using this threshold if the normal range is missing.

Measurements flagged as invalid by the laboratory will not be summarized or taken into account in the computation of PCSA values.

Handling of hypoglycemia event classification when some classification items are missing

Rule for handling missing data in classification items for hypoglycemia event will be provided in ADaM metadata.

Handling of missing data in the calculation of 7-point SMPG variables

For a given 7-point SMPG profile, at least 4 available measurements in the last 7 days are required to be taken into account in the statistical analyses (including the descriptive analyses at each time-point).

Handling of missing data in the calculation of average pre-breakfast SMPG,

At least 3 pre-breakfast (fasting) SMPG values in the last 7 days are required to be taken into account in the statistical analyses (including descriptive analyses at each time-point).

Handling of missing data in the calculation of insulin doses

At each visit, the average daily insulin doses (basal, mealtime, and total) will be calculated as the average of the daily insulin doses available in the week (7 days) before the visit.

No minimum number of available doses will be required.

For insulin doses in U/kg, if the body weight measurement is missing at a given visit, the last available measurement from previous visit will be used.

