9.2.2.3 Dose of basal and mealtime insulin

Patients will record their basal insulin and mealtime insulin dosing data (time and dose), including corrective doses, in the eDiary daily during the following periods:

- the randomization period after receiving of glucose meter and the eDiary device
- the treatment period up to Visit 9 (Week 12)
- at least over one week before each visit during the remainder of the treatment period until the EOT visit (Visit 12 – Week 24 or early treatment discontinuation)
- During the week of the follow-up period

The following endpoints will be considered: total insulin dose, basal insulin dose, mealtime/bolus as daily dose and u/kg.

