11.4.3.4.1 Hypoglycemia

The number and incidence of patients experiencing at least 1 hypoglycemic event will be presented per trial approach group and type of hypoglycemic event ([Section 9.2.4.4](#)) according to time of occurrence (nocturnal [ie, 00:00 to 05:59, by sleep status], any time of the day) during the treatment period. The Odds Ratio and its corresponding 95% CI of virtual group over traditional group for each hypoglycemic event will be estimated by a logistic regression model adjusted on randomization strata of screening HbA1c (<7.6%, ≥7.6%) and randomization strata of sites. This model will also estimate the Odds Ratio of virtual group and traditional group and its corresponding 95% CI.

The number and rate of hypoglycemic events (in patient-year of exposure) will be determined per trial approach group and type of hypoglycemic event ([Section 9.2.4.4](#)), according to time of occurrence (nocturnal [ie, 00:00 to 05:59, by sleep status], any time of the day) during the on-treatment period. For each hypoglycemic event, the rate ratio, and its corresponding 95% CI, of virtual group over traditional group will be estimated using an over-dispersed Poisson regression model adjusted on randomization strata of screening HbA1c (<7.6%, ≥7.6%) and randomization strata of site.

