2.3.2 Safety population

The safety population is defined as all randomized patients who did actually receive at least one dose of IMP, regardless of the amount of IMP administered.

In the event of patients having followed a trial approach that differed from the one assigned according to the randomization schedule, the safety analyses will be conducted according to the trial approach group assigned by randomization.

Patients will not be considered exposed if there is documented evidence that patients have not taken the study drug:

- If a patient is dispensed IMP and is lost to follow-up without any documented evidence, the patient will be considered exposed and included in the safety population.
- Randomized patients for whom it is unclear whether they took the study medication will be included in the safety population as randomized.

In addition:

- Nonrandomized but treated patients (or treated before being randomization (if any)) will not be part of the safety population; however, their safety data will be presented separately.
- For patients following more than one study approach (virtual and traditional), the patient will be analyzed in the study conduct approach group as randomized.

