2.4.3.1 Extent of investigational medicinal product exposure

The extent of IMP exposure will be assessed by the duration of IMP exposure.

The duration of exposure to the IMP during the study will be the total number of days of administration of IMP, ignoring temporary drug discontinuation (see [Section 2.5.3](#) for calculation in case of missing or incomplete data) and is defined as:

(Date of the last IMP administration – date of the first IMP administration) + 1

Duration of IMP exposure will be summarized descriptively as a quantitative variable (number, mean, SD, median, minimum, and maximum). In addition, duration of treatment exposure will also be summarized categorically by numbers and percentages for each of the following categories and cumulatively according to these categories:

- up to 4 weeks.
- >4 to 8 weeks.
- >8 to 12 weeks.
- >12 to 16 weeks.
- >16 to 20 weeks.
- >20 to 22 weeks.
- >22 to 23 weeks.
- >23 to 24 weeks.
- >24 weeks.

Additionally, the cumulative duration of treatment exposure will be provided, defined as the sum of the duration of treatment exposure for all patients, and will be expressed in patient years.

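### SAP 2.5.3 leaves exposure missing when the e-CRF last-dose date is absent, so patients lost without that date stay in the safety population but supply no person-time, exposure or compliance, and the hypoglycemia rate is left undefined for them

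*SAP*

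**What the plan says.** **Exposure.** SAP 2.4.3.1 counts days from first to last IMP administration, both included, and refers missing data to SAP 2.5.3. There the last-dose date has one source, the end-of-treatment e-CRF page. "If this date is missing, the exposure duration should be left as missing". The date also "should not be approximated by the last returned package date".

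**Who is analyzed.** For someone dispensed IMP and then lost with nothing documented, SAP 2.3.2 says "the patient will be considered exposed and included in the safety population". Exposure, compliance and hypoglycemia are all summarized on that population.

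**What depends on exposure.** Compliance (SAP 2.4.3.3) divides by exposure duration and allows no imputation. The hypoglycemia rate is per patient-year (SAP 2.4.5.1). Protocol 11.4.3.4.1 names the denominator: "The number and rate of hypoglycemic events (in patient-year of exposure) will be determined per trial approach group". The treatment-emergent period closes two days after the last injection (SAP 2.1.4), so it has no defined end when that date is missing.

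**What other record exists.** Under Protocol 9.2.2.3, "Patients will record their basal insulin and mealtime insulin dosing data (time and dose), including corrective doses, in the eDiary daily" through Week 12, and for at least the week before each visit after that. SAP 2.4.3.2 and 2.5.4 confirm that these doses are transferred to the clinical database.

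**What will be reported.** The opening of SAP section 2 states that the trial stopped with 15 patients randomized and that only basic descriptive statistics will be produced.

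**The concern.** A patient in the safety population with missing exposure adds nothing to the patient-years. If that patient's events are still counted, the crude rate has a numerator and a denominator built from different people, and it is biased upward. If the events are not counted, the patient disappears from the rate. Either way, the patient is also absent from the exposure categories, the cumulative patient-years and the compliance summaries, including the share below 80%.

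This matters more than usual here because hypoglycemia, medication compliance and retention are all outcomes set side by side for the two approaches. Retention is one of the things that remote conduct might change, so equal loss in the two arms cannot be taken for granted. The SAP leaves the numerator open, so two programmers following it could produce different rates from the same data.

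**Working it through.** The documents state no hypoglycemia rate, person-time or loss-to-follow-up figure, so there is no plan figure to reproduce on this point. The stated 0.37% precision concerns HbA1c and plays no part.

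**Step 1: is the numerator fixed by the text?** No sentence settles it for a missing last-dose date. The nearest guide is the SAP 2.5.3 rule for a missing *first*-dose date. Under that rule, events from randomization onward count as emergent while exposure stays missing, which is the same mismatch. That suggests events are kept, but does not establish it. Both readings are therefore carried forward.

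**Step 2: events kept, person-time dropped.** Inputs: 24 weeks of treatment (SAP 1.4). Assumptions: a share *f* of the arm is lost with no e-CRF date, at mean week *w*; the event rate is constant; everyone else completes.

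Inflation = [(1 − f) × 24 + f × w] / [(1 − f) × 24] = 1 + f × w / [(1 − f) × 24]

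- f = 5%: 1 + 0.05 × 4 / 22.8 = 1.009 at week 4; 1 + 0.05 × 20 / 22.8 = 1.044 at week 20.
- f = 10%: 1 + 0.4 / 21.6 = 1.019 at week 4; 1 + 1.2 / 21.6 = 1.056 at week 12; 1 + 2.0 / 21.6 = 1.093 at week 20.

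**Step 3: the trial as it ended.** With 15 randomized 1:1, assume arms of 7 and 8 and one affected patient.

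- Arm of 8: 1 + 4 / (7 × 24) = 1.024 at week 4; 1 + 12 / 168 = 1.071 at week 12; 1 + 20 / 168 = 1.119 at week 20.
- Arm of 7: 1 + 4 / (6 × 24) = 1.028 at week 4; 1 + 20 / 144 = 1.139 at week 20.

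**Step 4: effect on the comparison.** The rate ratio is multiplied by the ratio of the two inflation factors.

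- Equal loss at equal times: factor 1.00.
- 15% virtual against 5% traditional, week 12: 1.0882 / 1.0263 = 1.06. From week 4 to week 20 the range is 1.02 to 1.10.

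**Step 5: both readings compared.** A simulation (2,000 runs, 75 per arm) assumed a true rate of 20 per patient-year in both arms, with 11 virtual and 4 traditional patients lost at week 12.

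| Treatment of lost patients | Virtual | Traditional | Ratio |
|---|---|---|---|
| Full person-time | 20.0 | 19.9 | 1.00 |
| Events kept, person-time dropped | 21.7 | 20.5 | 1.06 |
| Dropped from both | 20.0 | 19.9 | 1.00 |

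The third row uses 135 of 150 patients. It shows no bias because the simulated lost patients have the same underlying rate as the rest.

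**The case against.** The strongest reply is that the bias mechanism is not written down. A reader might cite "By default all adverse events/hypoglycemia are emergent except if additional information allows to classify otherwise" as proof that events are kept, but that sentence stands under missing or partial *onset* dates. The opening of SAP 2.5.3 also accepts that analyses may omit patients with missing data, so full exclusion is a fair reading, and under it the crude rate need not be biased. This stands, and it is why the point is put conditionally.

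Other stronger inferences also go beyond the documents:

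- *That the rate-ratio model drops these patients.* This would follow from a log-exposure offset, but neither document names one. After early termination the model is probably not run.
- *That every lost patient is affected.* Protocol 8.7.1 and 10.1.3 have doses asked about at each contact, the flow chart calls for end-of-treatment assessments after premature discontinuation, and Protocol 10.3.5 requires recontact efforts. Only patients for whom all of this fails lack a date.
- *That the shortest-treated patients vanish.* Early discontinuers with a recorded date remain, and a patient lost late without one does not.

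Size is a fair objection too. In an arm of 8, seven completers give 7 × 168 / 365.25 = 3.22 patient-years. At an assumed 20 events per patient-year that is about 64 events, with Poisson error of about 12% (1/√64) before overdispersion, which is larger than the 7.1% inflation.

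A last argument is that leaving exposure missing is a deliberate, consistent choice, and that differential loss is already visible in the disposition tables and Kaplan-Meier plots. Those displays show who left. They do not restore person-time or say what the rate contains.

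**Conclusion.** The point holds in a limited form. It is certain that a patient lost without an e-CRF last-dose date stays in the safety population while supplying no patient-years, exposure duration or compliance, and that dated diary doses exist which could fill most of the gap. It is also certain that the SAP does not define the rate numerator for that patient.

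Inflation of the crude rate is conditional on the events being kept: about 2% to 9% at 10% affected, or about 2% to 14% for one patient in an arm of 7 or 8. These figures rest on an assumed share lost, an assumed time of loss and a constant event rate. A reader might infer a built-in bias against one approach. The documents do not support that, since they give no loss rates by arm and equal loss leaves the ratio unchanged. If the patients are excluded altogether, the cost is lost data, with bias only if their event rate differs from that of the patients kept.

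With 15 patients and descriptive reporting, what is affected is the exposure, compliance and crude-rate tables. This is a cheap improvement worth making, not a threat to the trial's conclusions.

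**What to change.** In SAP 2.5.3:

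1. If the e-CRF last-dose date is missing, use the last e-diary date with a non-zero IMP dose, or failing that the last contact at which IMP use was confirmed. Apply it to exposure, person-time and compliance. Keep the ban on the returned-package date.
2. In the per-patient-year rate, use the same patients and the same time window in numerator and denominator. Name that person-time as the offset in any model that is fitted.
3. Keep the conservative emergent-by-default classification for incidence tables and listings. The derived date should limit only the rate calculation, so that no reported event is discarded.
4. Report by arm how many patients had a date derived this way.

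The cost is one SAP rule and some programming on data already transferred. The downside is that after Week 12 visits are four weeks apart and the diary is required only in the week before each. A patient lost in between could have the last dose understated by up to about 4 − 1 = 3 weeks. That still recovers most of the person-time, whereas the present rule recovers none.
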